3.2.3 Safety Population

The Safety Population will include all subjects who are randomized and have received at least one dose of study drug, including all subjects who have not yet completed the Week 26 visit. All

safety data will be analyzed using the Safety Populations according to the actual treatment received.

Notations for Treatment Periods

Treatment Period A: Initial 26-week placebo-controlled, double-blind treatment period, Day 1 – Week 26

Treatment Period B: Week 26-Week 52, the Avacopan treatment period plus 8 Weeks of Followup, Week 26 to End of Study (EOS)

3 Safety Populations for this study:

- 1. The Safety Population in the Treatment Period A is defined as all subjects who received at least one dose of blinded Investigational Drug during Treatment Period A.
- 2. The Safety Population in Treatment Period B is defined as all subjects who received at least one dose of Avacopan during Treatment Period B.
- 3. The All Avacopan Treated Population is defined as all subjects who received at least one dose of Avacopan in the study.

3.2.4 Per Protocol Population

The Per Protocol (PP) Population will consist of ITT subjects who receive at least one dose of study drug and do not have protocol deviations that could significantly affect the interpretation of the results for the primary endpoints.

The following aspects will be relevant for consideration of subjects to be excluded from the PP analysis:

- Subjects with significant protocol deviations regarding inclusion and exclusion criteria that may impact evaluation of the primary endpoints.
- Subjects who did not have week 26 with renal biopsy
- Subjects with significant lack of compliance of study medication administration (avacopan /placebo) defined as: All subjects who were <75% compliant overall during the 26-week Treatment Period A based on study medication accountability records.
- Subjects with introduction of new treatment medications for C3G such as Mycophenolate mofetil (MMF) and glucocorticoids after the screening biopsy and prior to week 26 renal biopsy such that the screening renal biopsy is done off immunosuppressant medication and the week 26 renal biopsy is done on immunosuppressant medication.
- Subjects with clinically significant increase in immunosuppressant dose (MMF, Prednisone) during the study that may impact renal biopsy results significantly.
- Subjects whose data could have been significantly impacted by COVID-19.

Subjects to be excluded from the PP Population will be identified and documented prior to the database lock and unblinding for analysis. A subject's data could be partially excluded from analysis depending on when the deviation occurred. For example, if a deviation occurred during the avacopan treatment period that did not impact the data from the double-blind period, only the data during the avacopan treatment period will be excluded.

3.2.5 C5b-9 Patient Populations

3.2.5.1 C5b-9 Elevated Stratum

This population includes all subjects enrolled under the C5b-9 elevated stratum (C5b-9 >244 ng/ml), and is the primary target population for analysis.

3.2.5.2 C5b-9 Non-Elevated Stratum

This population includes all subjects enrolled under the C5b-9 non-elevated stratum (C5b-9 <=244 ng/ml). As the sample size in this stratum is small, only summary results will be provided, no test between treatment groups will be done

3.2.5.3 Combined Population

The two strata combined (including both elevated and non-elevated C5b-9 strata) will be considered the secondary population for the primary analysis.

4 ANALYSIS OF DISPOSITION AND SUBJECT CHARACTERISTICS

4.1 Disposition and Analysis Populations

Subjects who withdrew early from the study with the reasons for early withdrawal, and subjects who prematurely discontinued study drug with the reasons for discontinuation will be presented by treatment group. These treatment groups include the number of subjects who were screened, screen failed (by reason), randomized, completed Treatment Period A at Week 26, and who completed the Avacopan treatment period. Additionally, the number of subjects in each analysis population will be presented by treatment group.

4.2 **Protocol Deviations**

Significant protocol deviations, i.e., those pertaining to Good Clinical Practice (GCP) violations and those that may affect the efficacy evaluation, will be captured in the Study Management System as CSR Reportable deviations. These significant deviations will be listed and summarized by category for all randomized subjects. These deviations will be reviewed prior to database freeze to determine the potential impact on the interpretation of the efficacy outcomes. The effect of major protocol deviations will be assessed by conducting per-protocol analyses (see section 3.2.4). This will be determined and documented prior to unblinding the study for the primary analysis and then again at final database lock, if applicable. Deviations related to COVID-19 will be classified as such and may be summarized and/or listed separately.

4.3 Demographics and Baseline Characteristics

Demographics and baseline characteristics will be described separately for all subjects who enrolled in Treatment Period A and subjects who enrolled in Treatment Period B. These will also be described separately for strata of elevated C5b-9 blood level and non-elevated C5b-9 blood level in the ITT population. This description will include subject baseline characteristics and demographic data (age, sex, race, ethnicity, weight, height, body mass index, viral test results, C3G disease type and duration [from time of first diagnosis based on renal biopsy in months], eGFR, proteinuria [UPCR], complement marker levels, and urinary MCP-1:creatinine ratio) will be listed by study center and subject number, and will also be summarized by treatment group for all randomized subjects.

4.4 Concomitant Medications

All prior and concomitant medications (including medications taken for C3G) will be listed and summarized by Anatomic Therapeutic Chemistry (ATC) classification. The numbers and percentages of subjects taking prior and concomitant medications will be summarized by treatment group, ATC class, and preferred term for the Randomized Population. Concomitant medications will be coded using the World Health Organization (WHO) Drug Dictionary (Sep 2016E B2).

Prior medications are defined as any medication taken prior to the first dose of study medication. Concomitant medications are defined as any medication taken on or after the first dose of study medication. A medication can be classified as both prior and concomitant if it started during the screening period and continued into the treatment period. Prior medications were to be recorded for any medication taken for C3G within 12 months of screening or taken for reasons other than C3G within 6 months of screening.

4.4.1 Non-Study Supplied Treatments for C3G

Non-study specified or supplied treatments for C3G will be listed and summarized by treatment group. These treatments include, but are not limited to, non-protocol allowed or increased doses of the following medications: glucocorticoids, mycophenolate (MMF), , angiotensin-converting enzyme (ACE) inhibitors, angiotensin receptor blockers (ARB), renin-angiotensin-aldosterone system (RAAS) blockers, aldosterone, cyclosporin, calcineurin inhibitors, eculizumab and other anti-C5 antibodies, strong inducers/inhibitors of CYP3A4 enzyme (Inducers :carbamazepine, phenobarbital, and phenytoin, rifampin, or St. John's wort and Inhibitors: boceprevir, clarithromycin, conivaptan, indinavir, itraconazole, ketoconazole, lopinavir/ritonavir, mibefradil, nefazodone, nelfinavir, posaconazole, ritonavir, saquinavir, telaprevir, telithromycin, and voriconazole) or other experimental or immunosuppressive drugs.

5 ANALYSIS OF EFFICACY

The overall efficacy hypothesis in this study is that avacopan treatment will be effective in treatment of subjects with C3G based on improvement in renal histology (C3G histologic index of activity).

5.1 Covariates and Subgroups

The analysis of the efficacy endpoints may be performed by the following variables in the form of covariate analysis and/or subgroup analysis:

Stratification factors [1]:

- Subjects with elevated C5b-9 levels (>244 ng/mL)
- Subjects with non-elevated C5b-9 levels ($\leq 244 \text{ ng/mL}$)
- Disease type C3GN
- Disease type DDD
- Subjects who received a renal transplant
- Subjects who have not received a renal transplant

[1] The stratification factor values as collected in the electronic case report forms (eCRFs) will be used for all stratified efficacy analyses, subgroup analyses and summaries of baseline characteristics. If missing, actual stratification factor will be used. Stratification groups with low counts may be combined.

Subgroups and Covariates

- Sex
- Baseline BMI
- Age at diagnosis of C3G
- Age at randomization; a subgroup analysis will be performed in 12 to 17 year-old subjects, if feasible.
- Duration of C3G
- Subject's race and ethnicity (if plausible)
- Baseline C3G Histologic Index for disease activity
- Baseline C3G Histologic Index for disease chronicity
- Baseline eGFR
- Baseline UPCR
- Baseline urinary MCP-1:creatinine ratio
- Baseline C5b-9, C5a, and C3a
- Geographic distribution (North America vs. Rest of World)

5.2 Primary Efficacy Analysis

The primary efficacy endpoint is the percent change from baseline to Week 26 in the C3G Histologic Index for disease activity. The C3G Histologic Index for disease activity can assume a score from 0-21. See Section 2.3.4 for further details on the calculation of C3G Histologic Index for disease activity.

Statistical Hypothesis Testing and Procedure

• The null hypothesis (H0) is that the avacopan group is not different from the placebo group when comparing the percent change from baseline to Week 26 in the C3G Histologic Index for disease activity.

• The alternative hypothesis (H1) is that the avacopan group is different from the placebo group when comparing the percent change from baseline to Week 26 in the C3G Histologic Index for disease activity.

Numbers, means, median, standard deviation, standard error of means, minimum and maximum will be presented by treatment group and study visit. Avacopan and placebo groups will be compared by Analysis of Covariance (ANCOVA) with treatment group as factor and baseline C3G Histologic Index for disease activity as a covariate. The LS mean estimate and corresponding 95% confidence interval (CI) will be estimated for the treatment main effect. The heterogeneity of the treatment effect across disease diagnoses and renal transplant strata may be investigated through subgroup analyses.

As there are no data available to access the possibility of non-normality distribution of percent change or change from baseline, normality distribution tests will be performed for both percent change and change from baseline. It is possible that the normality test would not hold for percent change from baseline or change from baseline or both. In this case, the following is the analysis procedures for the primary efficacy endpoint.

• If the test for normality fails for percent change from baseline at α level of 0.10 but not change from baseline, change from baseline will be used as the primary endpoint;

• If the test for normality fails for both percent change and change from baseline at α level of 0.10, percent change from baseline will be used as the primary endpoint, but non-parametric methodology will be used for the primary endpoint analysis. The van Elteren's test will be applied to test the percent change from baseline endpoint.

The treatment effect based on the baseline complement profile of subjects may also be investigated.

The SAS code to generate the Analysis of Covariance will be similar to the following:

See Appendix 12.3 for the SAS code to perform van Elteren's test to compare the two treatment groups using the imputed datasets.

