2.2.2 Stratification

Subjects will be stratified by elevated or non-elevated levels of C5b-9, and then randomized using a minimization algorithm to receive 30 mg avacopan twice daily or avacopan-matching placebo twice daily for 26 weeks in a double-blind manner:

Both strata, (i.e., C5b-9 levels >244 ng/ml and \leq 244 ng/mL) will include approximately 44 subjects; each level will have approximately 22 subjects randomized (1:1) to the avacopan or avacopan-matching placebo arm, respectively. However, enrollment for the stratum with C5b-9 levels \leq 244 ng/ml could terminate early if subject enrollment in the other stratum (C5b-9 level >244 ng/mL) reaches target enrollment first.

To obtain balance across treatment groups, eligible subjects within each of the C5B-9 level strata will be further stratified based on two factors:

- 1. C3 glomerulonephritis (C3GN) or Dense Deposit Disease (DDD), and
- 2. Whether the subject has received a kidney transplant or not.

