3 STATISTICAL METHODOLOGY

3.1 General Considerations

For efficacy analysis, to control for the Type I error rate, a gate-keeping procedure will be applied for the analysis of the primary efficacy endpoint (percent change in C3G Histologic Index for disease activity). The primary endpoint will be tested in the elevated C5b-9 stratum first with a two-sided $\alpha = 0.05$. If this test reaches statistical significance, then the primary endpoint will be tested in the combined C5b-9 strata (including both elevated and non-elevated C5b-9 strata) with a two-sided $\alpha = 0.05$. If the test in the elevated stratum fails to reach statistical significance, then the test in the combined C5b-9 strata will only be performed as an exploratory analysis. The statistical analysis for the secondary endpoint (C3G Histologic Index for disease chronicity) will be tested at a 0.05 α -level only if the primary endpoint in the same stratum reaches statistical significance.

Data will be summarized descriptively by treatment group as well as separately for the elevated C5b-9 stratum and combined strata. For continuous variables, numbers, means, medians, ranges, standard deviations, and standard error of means will be calculated. Geometric means will be calculated for UACR and urinary MCP-1:creatinine ratio, and other data that are not normally distributed. Frequency counts and percentages will be presented for categorical variables. Listings of raw and derived data will be included as part of an appendix to the CSR.

In analysis tables and listings, the two treatment groups will be referred to as

- 'Placebo', referenced in the protocol as Group A (placebo)
- 'Avacopan', referenced in the protocol as Group B (avacopan)

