5.2.1 Primary Analysis

The primary analysis will be based on the ITT population in the elevated C5b-9 stratum (>244 ng/ml). The primary analysis is based on percent change from baseline to Week 26 during the double-blind treatment period and will be analyzed using the ANCOVA analysis methods described above. Both percent change from baseline and change from baseline will be summarized and analyzed with percent change from baseline being the primary efficacy endpoint.

Multiple Imputation Method

Missing data used to calculate the primary endpoint will be handled using the Missing at Random (MAR) multiple imputation method. The multiple imputation procedure will be conducted in two parts using SAS[®] PROC MI and PROC MIANALYZE.

The primary analysis will be carried out by imputing missing data for the 7 lesions that comprise the Histological Index for Disease Activity. The multiple imputation model will include the two stratification factors (disease type [C3G or DDD] and kidney transplant status [Y/N]), treatment group, in addition to values at each visit from baseline through week 26. For each lesion component, 100 'complete' datasets will be generated using SAS[®] PROC MI. The seeds for the imputation will be specified as '12061', '36102', '94218', '20949', '60137', '80230' and '59137', for imputation of 7 lesion activity scores, respectively. Imputed individual lesion component scores will then be classified into scale scores (e.g., leukocyte infiltration % involvement = 29% would translate to a scale score of 2). The 'complete' datasets for the individual components of the lesion activity scores will be merged by imputation number and summed to calculate the Histological Index for Disease Activity and creation of 100 'complete' datasets for evaluation of activity scores.

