Multiple imputation will be used to impute missing data and will be implemented using SAS® PROC MI: Missing data may be the result of missing lesion components for calculation of C3G Histological Index of Disease Activity or Disease Chronicity or due to subjects discontinuing the study prior to Week 26 or Week 52. Missing at random (MAR) will be assumed. The primary analysis will be carried out by imputing missing data for the 7 lesions that comprise the Histological Index for Disease Activity and separately for the 4 lesions that comprise the Histological Index for Disease Chronicity. The multiple imputation model will include the two stratification factors (disease type [C3G or DDD] and kidney transplant status [Y/N]), treatment group, in addition values at each visit from baseline through week 26. If the model fails to converge, exclusion of stratification factors may be considered.

For each lesion component, 100 'complete' datasets will be generated using SAS® PROC MI. Imputed individual lesion component scores will then be classified into scale scores (e.g.,

leukocyte infiltration % involvement = 29% would translate to a scale score of 2). The 'complete' datasets for the individual components specific to disease activity and disease chronicity separately, will be merged by imputation number and summed to calculate the Histological Index for Disease Activity and Disease Chronicity and creation of 100 'complete' datasets for evaluation of activity and chronicity scores.

The results from the 100 fitted models will be combined using SAS® PROC MIANALYZE. The estimate of the treatment difference and standard error from the analysis will be analyzed by PROC MIANALYZE to obtain the overall estimate of treatment difference, as well as the confidence interval and p-value for the hypothesis testing. This will be done separately for Histological Index for Disease Activity and Histological Index for Disease Chronicity

The steps to carry out the primary multiple imputation and analysis are described below:

The 6 lesions in disease activity and 2 lesions in disease chronicity with continuous results will be imputed using SAS code below.

```
/* Imputation at Week 26 */
Proc MI Data= num_org Seed= Seedno nimpute= 100
    minimum= . . 0
    maximum= . . 100
    Out= mum_mi26;
    by TRT01PN;
    class DISTYPE RENTRANS;
    var DISTYPE RENTRANS BL W26;
    monotone reg(W26/details) ;
Run;
```

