     TRT01PN = Treatment Group (Placebo/Avacopan)
*** Perform ANCOVA;
PROC MIXED DATA= EFFI;
     By Imputation ;
     Class TRT01AN(ref='1');
     Model Response = TRT01AN Base / solution cl ddfm = KR
                   residual OUTP = ano_res ;  * studentized residual ;
     Lsmeans TRT01AN / Alpha=0.05 cl diff ;
     ODS Output LSMEANS = ano lsm
                    Diffs = ano diff;
RUN;
*** Combine result;
PROC MIANALYZE DATA = ano lsm;
     By TRT01AN;
     Modeleffects Estimate;
     Stderr;
     ODS Output
           ParameterEstimates = miana_lsm;
RUN;
PROC MIANALYZE DATA = ano diff;
     By TRT01AN;
     Modeleffects Estimate;
     Stderr;
     ODS Output
           ParameterEstimates = miana diff;
RUN;
*** Normality Test;
PROC UNIVARIATE DATA = ano_res Normaltest;
     Class Imputation ;
     Var StudentResid;
     ODS Output
           TestsForNormality = res SW (Where=(Test="Shapiro-Wilk"));
Run;
*** Select the minimum P-value from Shapiro-Wilk test among all imputation;
```

For the primary analysis of change from baseline to Week 26 in C3G Histological Index of Disease Activity and Disease Chronicity, the normality test is performed on the imputed data using the Shapiro-Wilk test where the lowest p-value is selected. If the p-value is < 0.01, normality is rejected, van Elteren's test is used for the treatment comparison. The steps to carry out the analysis are detailed below.

```
Note:
     EFFI = Efficacy Analysis Dataset with multiple imputation
     Response = categorical variable of interest in analysis
     DISTYPE = Disease Type (C3GN or DDD)
     RENTRANS = Renal Transplant Status (Y/N)
     TRT01PN = Treatment Group (Placebo/Avacopan)
*** Van Elteren's Test by each Imputation;
Proc Freq Data= EFFI;
     By Imputation ;
     Table DISTYPE*RENTRANS*TRT01PN*Response / CMH Scores= modridit;
     Ods Output
          CMH= cmh RMS (Where=(AltHypothesis="Row Mean Scores Differ"));
Run;
*** Apply Wilson-Hilferty transformation to the CMH statistic and standardize the
resulting normal variable;
DATA cmh wh;
     SET cmh RMS;
     cmh value wh = ((VALUE/DF)**(1/3) - (1-2/(9*DF)))/SQRT(2/(9*DF));
     cmh sterr wh = 1.0;
RUN;
*** Proc MIANALYZE;
PROC MIANALYZE DATA = cmh wh;
     Modeleffects cmh value wh;
     Stderr cmh_sterr_wh;
     ODS Output
           ParameterEstimates = cmh miana;
RUN;
```

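### The primary ANCOVA and the MMRMs leave out the two minimisation factors, and the combined-strata test also leaves out C5b-9 stratum, so precision is lost if these factors are prognostic

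*SAP*

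**What the plan says.** **Allocation.** Patients are first divided by C5b-9 level. SAP 2.2.2 then says: "To obtain balance across treatment groups, eligible subjects within each of the C5B-9 level strata will be further stratified based on two factors". The two factors are C3GN versus DDD and transplant versus none. Protocol 3.1, 3.2 and 5.2 describe the same scheme, 1:1 by minimisation.

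**Primary model.** SAP 5.2 has the two arms "compared by Analysis of Covariance (ANCOVA) with treatment group as factor and baseline C3G Histologic Index for disease activity as a covariate". Protocol 8.7.5 specifies the same model, and the code in SAP Appendix 12.3 agrees: "Model Response = TRT01AN Base / solution cl ddfm = KR". SAP 5.2.1 confines this test to the elevated C5b-9 stratum.

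**Second gated test.** If the first test succeeds, SAP 3.1 says, "then the primary endpoint will be tested in the combined C5b-9 strata (including both elevated and non-elevated C5b-9 strata"). SAP 5.2.2 gives it the same analysis as the primary one, so it has no C5b-9 term.

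**Other models.** The UPCR MMRM in SAP 5.3.1.1 has treatment, visit, their interaction and baseline. SAP 5.3.2, 5.3.5 and 5.3.6 reuse it for eGFR, urinary MCP-1 and quality of life.

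**Where the factors do appear.** Appendix 12.3 uses disease type and transplant, but not C5b-9, in the imputation code ("var DISTYPE RENTRANS BL W26") and in the van Elteren table ("Table DISTYPE*RENTRANS*TRT01PN*Response / CMH Scores= modridit"). SAP 5.1 lists all three factors, but only says that analyses "may be performed by the following variables in the form of covariate analysis and/or subgroup analysis".

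**The concern.** Minimisation removes most of the chance imbalance between arms on disease type and transplant. If those factors are related to the outcome, the treatment estimate varies less from trial to trial than it would under simple randomisation. A model without them leaves their variance in the residual, so it reports a standard error that is too large for the design used. The test then rejects less often than 5% under the null, the interval is too wide, and some power is lost.

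The same holds for C5b-9 once the strata are pooled, because arms are balanced within each stratum by design. C5b-9 is constant in the primary test, so its absence matters only in the combined analyses.

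The plan is also uneven. Whether the primary comparison respects the allocation factors depends on a normality test: the ANCOVA ignores them, while the van Elteren fallback stratifies by them. The permissive wording of SAP 5.1 does not settle which model counts.

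**Working it through.** **1. The plan's own sample size.** Inputs from SAP Section 9: difference 35, SD 34, two-sided alpha 0.05, power 90%. The normal approximation gives n = 2 × 34² × (1.960 + 1.282)² / 35² = 19.8, so 20 per arm. With the non-central t, 21 per arm gives power 0.902 and 22 gives 0.915. The stated 22 is reproduced.

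**2. Inputs for the check.** I take 21 per arm: the 44 planned for the elevated stratum, less the 2 patients whom SAP 8.1 says will not reach Week 26, split evenly. SD is 34. R² is the share of variance left after baseline that disease type and transplant explain. The documents do not give it, so I use 0, 0.05, 0.10 and 0.20.

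**3. Formulas, arms exactly balanced on the factors.**
- The unadjusted SE targets 34 × √(2/21) = 10.49, so the half-width is 2.023 × 10.49 = 21.2. The true SD of the estimate is 10.49 × √(1 − R²).
- True size of the unadjusted test: 2 × P(t39 > 2.023/√(1 − R²)). At R² = 0.10 this is 2 × P(t39 > 2.132) = 0.039.
- Unadjusted power: non-central t, 39 df, non-centrality d/(10.49 × √(1 − R²)), critical value 2.023/√(1 − R²).
- Adjusted power: the same non-centrality, 37 df, critical value 2.026. The adjusted half-width is 2.026 × 10.49 × √(1 − R²).

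| R² | True size, unadjusted | Half-width, adjusted | Change in width | Power at 35, unadjusted to adjusted | Power change at 25 (assumed), points |
|---|---|---|---|---|---|
| 0 | 0.050 | 21.3 | 0.2% wider | 0.902 to 0.901 | −0.1 |
| 0.05 | 0.045 | 20.7 | 2.4% narrower | 0.907 to 0.915 | +1.8 |
| 0.10 | 0.039 | 20.2 | 5.0% narrower | 0.913 to 0.928 | +3.8 |
| 0.20 | 0.029 | 19.0 | 10.4% narrower | 0.925 to 0.953 | +8.0 |

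**4. Imperfect balance.** I simulated 10,000 trials of 42 patients, with minimisation at assignment probability 0.8, 30% DDD and 20% transplant (all assumed), and both factors contributing equally to R². For the four values of R², the unadjusted size is 0.049, 0.045, 0.042 and 0.035, and the adjusted size is about 0.051. Adjustment changes power at 35 points by −0.3, +1.0, +1.9 and +3.7 percentage points. A second simulation, with 44 patients, 25% DDD and 15% transplant, gives unadjusted size 0.039 at R² = 0.10 and 0.036 at R² = 0.20.

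**5. Combined test.** Assume 42 elevated patients plus 10, 20 or 44 non-elevated, and let q be the non-elevated share. With arms balanced within stratum, the variance seen by the model without stratum is 34² + q(1 − q) × gap², where gap is the difference in mean response between strata. With 20 non-elevated patients and a gap of 20, this is 1156 + 0.2185 × 400 = 1243.

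| Gap | Unadjusted size (10, 20, 44 patients) | Interval with stratum added |
|---|---|---|
| 0 | 0.050 throughout | at most 0.1% wider |
| 20 | 0.044, 0.042, 0.041 | 2.5%, 3.5%, 4.0% narrower |
| 34 | 0.036, 0.031, 0.029 | 6.9%, 9.4%, 10.5% narrower |

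**The case against.** The treatment-plus-baseline model is prespecified identically in protocol and SAP, it is valid, and power at the planned effect is at least 0.90 by formula whatever the R². That stands, and it limits the point to efficiency.

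The larger gains need strong prognostic effects. With 30% DDD and 20% transplant sharing R² equally, R² = 0.20 requires gaps of 34 × √(0.10/0.21) = 23.5 points between disease types and 34 × √(0.10/0.16) = 26.9 points by transplant. Both are large beside a planned treatment effect of 35. R² = 0.10 still needs about 17 and 19. The title of the C3G cohort study in both reference lists suggests that the two disease types run a similar course, which is a weak hint against a large disease-type effect. The 8-point gain also assumes a true difference of 25, which the documents do not state, and the largest combined-test figures assume 44 non-elevated patients although SAP 3.2.5.2 calls that stratum small. All of this is fair. The upper rows mark the end of a range and are not forecasts.

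The MMRM endpoints lie outside the gated sequence and no loss was calculated for them. Leaving C5b-9 out of the combined imputation model is a missing-data matter that the variance formulas do not cover, and the statement that there is no bias does not extend to it. Both follow the same principle but are less firmly supported.

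Sparse transplant cells are a real difficulty in about 42 patients. That calls for a fixed rule for sparse levels and does not justify leaving out every factor.

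**Conclusion.** The concern holds. The models named for the primary test, the combined gated test and the MMRMs do not use the factors on which patients were allocated, and SAP 5.1 permits adjustment without specifying it. The consequence is a conservative test and a wider interval than necessary, by an amount that depends on an R² the documents do not give. At R² = 0.05 to 0.10 the interval could be 2 to 5% narrower, and power at the planned effect would rise by about 1 to 2 percentage points. If the true effect is smaller than planned, the gain is larger. At R² = 0 almost nothing is lost by adjusting.

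This is a change that should be made because it is cheap and its downside is small. The trial is valid without it. Confidence is medium: the omissions are certain, but their cost is known only as a range.

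**What to change.** - Add disease type and transplant as main effects to the activity and chronicity ANCOVAs and to the MMRMs.
- In every combined-strata analysis, also add C5b-9 stratum to the ANCOVA, the MMRM, the van Elteren strata and the imputation model.
- Fix a rule for sparse levels from blinded counts before unblinding: drop or pool transplant first, then disease type, and keep C5b-9 in all combined analyses. This replaces the open options in SAP 5.1 and Appendix 12.3.
- Keep the treatment-plus-baseline model as a sensitivity analysis.

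The cost is SAP wording, one model line per analysis and an entry in SAP Section 10. Protocol 8.7.5 carries the same model, so the sponsor must also decide whether this is a change to a principal feature that needs an amendment under protocol Section 8. Disease type and transplant are already in the datasets for imputation and van Elteren. The primary model uses two more degrees of freedom and the combined model three. If the factors are not prognostic, the power lost is about 0.1 percentage point by formula and 0.3 to 0.5 in simulation.
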